#### 1. Study Device

Category	Instrument and Apparatus(07)Visceral Function Substitute Device
Generic Name	Stent graft with heparin for blood vessel
Commercial Name	GORE® VIABAHN® Endoprosthesis

#### 2. Purpose of surveillance study

To confirm device efficacy and safety in the clinical setting after the launch of the GORE® VIABAHN® Endoprosthesis (hereafter “VB device”) for the treatment of symptomatic peripheral arterial disease in the superficial femoral arteries.

#### 3. Planned number of subjects and its rationale

Planned number of subjects: A minimum of 250 cases (Enrollment will be continued until 250 patients with lesion length greater than or equal to 15 cm will be enrolled)

Rationale:

[REDACTED]

[REDACTED]

#### 4. Patients to be subjected to this surveillance study

Patients with symptomatic peripheral arterial disease in superficial femoral artery lesions 10cm or more in length with reference vessel diameters ranging from 4.0 to 7.5mm (hereafter, “study target patient”) and also other patients had treatments with VB device during the enrollment period in addition to the study target patient. The patients who have the treatment of traumatic or iatrogenic vessel injury in thoracic, abdominal, and pelvic arteries (except the aorta, coronary, brachiocephalic, carotid, vertebral and pulmonary arteries) with VB device are not included into this study.

#### 5. Planned number of institutions by department

The planned number of institutions: About 60 institutions which conclude a contract that adheres to GPSP ordinances after the study initiation, or use the GORE® VIABAHN® Endoprosthesis before conclusion of a contract that adheres to GPSP ordinances and NHG knows that information. This institutions includes the study sites for VJH-11-01 study.

The number of institutions of VJH-11-01 Pre-Market Study: 15 sites 3 departments (Vascular surgery department: 6 sites, Cardiovascular internal medicine department: 6 sites, Radiology department: 3 sites)

#### 6. Method of Surveillance Study

- 1) To make a written agreement between the participating institutions, NHG, and NHG’s outsourcing contractor on the surveillance study.
- 2) This survey will continuously enroll all patients treated for symptomatic peripheral arterial disease with this device in each of the participating institutions, except the patients who have the treatment of traumatic or iatrogenic vessel injury in thoracic, abdominal, and pelvic arteries (except the aorta, coronary, brachiocephalic, carotid, vertebral and pulmonary arteries) with VB device. The patients who have a treatment with VB device before conclusion of a contract will be enrolled to this study retrospectively.
- 3) The surveillance of the PAD patients who have a treatment with VB device is conducted in accordance with this protocol.
- 4) The surveillance of the patients who had a treatment with VB device for the disease except PAD is also

conducted in accordance with the contents stipulated in Attachment 1 of this protocol.

- 5) After one month from the procedure and on annually afterwards, the study doctor needs to submit the case report form with inputting the data to Electric Data Capture system that NHG indicates.
- 6) After one month from the procedure and on annually afterwards, representatives of NHG or the outsourcing contractor are to collect case report forms for the post-marketing surveillance study on which necessary items are filled out.
- 7) If any deficiencies of VIABAHN are recognized, the physicians responsible for the case or representatives of the outsourcing contractor will immediately report them to representatives of NHG and the GVP section of NHG will handle them appropriately.
- 8) From the approval date, an annual report will be made, reviewed, and approved by the Post-Marketing Surveillance Study team and the GVP section of NHG, and then submitted to PMDA.

## 7. Planned surveillance period

Total surveillance period: Six years and ten months

Sales preparation period: About five month

Enrollment period: About five months (until the 250 cases treated with 15cm of lesion lengths will be enrolled)

Follow-up period: For five years from procedure

CRF collection period, Analysis period and Data Fixation period: twelve months

## 8. Items to be investigated

### 8.1 Items to be investigated

The following items are investigated in each time window

#### 8.1.1 On the procedure day

- Patient background, pre-operative patient information, etc
- Device usage information
- Presence / absence of concurrent treatments and their detail if there was any
- Rutherford classification
- ABI
- Information on antiplatelet drug administration
- Adverse events and/or device deficiencies and their details (Thrombosis, TLR (Revascularization for restenosis or occlusion of the treatment lesion) , Stent graft occlusion, Stent graft stricture etc)

#### 8.1.2 At 1 month Follow-up visits

- Date of discharge
- Rutherford classification
- ABI (or TBI) (Presence / absence of patent of the treatment site)
- Information on antiplatelet drug administration
- Adverse events and/or deficiencies and details (Thrombosis, TLR, Stent graft occlusion, Stent graft stricture etc)

#### 8.1.3 At 12, 24months Follow-up visits

- Rutherford classification
- ABI (or TBI) (Presence / absence of patent of the treatment site)
- CDUS (Presence / absence of patent of the treatment site)
- Plain X-ray (Presence / absence of Stent fracture)
- Information on antiplatelet drug administration
- Adverse events and/or deficiencies and details (Thrombosis, TLR, Stent graft occlusion and Stent graft stricture etc)

#### 8.1.4 At 36, 48 and 60months Follow-up visit

- Rutherford classification
- ABI (or TBI) (Presence / absence of patent of the treatment site)

- CDUS (Presence / absence of patent of the treatment site)
- Plain X-ray (Presence / absence of Stent fracture)
- Adverse events and/or deficiencies and details (Thrombosis, TLR, Stent graft occlusion and Stent graft stricture etc)

Table 1: Examination schedule

Diagnostic Test	Procedure	1 month	12 months	24 months	36 months	48 months	60 months
Patient background and pre-operative patient information	X						
Date of discharge		X					
Device usage information	X						
Presence / absence of concurrent treatments and their detail if there was any	X						
Information on antiplatelet, anticoagulant drug administration	X	X	X	X			
Rutherford classification	X	X	X	X	X	X	X
ABI (or TBI)	X	X	X	X	X	X	X
CDUS			X	X	X	X	X
Plain X-ray			X	X	X	X	X
Adverse events and/or deficiencies and details	X	X	X	X	X	X	X

## 8.2 Focused survey items and concrete survey methods of the items

Focused survey item: Stent Fracture

Rationale:

[REDACTED]

[REDACTED]

[REDACTED]

## 9. Items and methods of analysis

Following endpoints for efficacy and safety and focused survey items will be aggregated

### 9.1 Efficacy:

#### 9.1.1 Primary assisted patency at 12 and 24 months

Primary assisted patency defined as hemodynamic evidence of flow through a device that had not required a TLR to restore flow after total occlusion. This will be calculated using Kaplan-Meier analysis and will be estimated at 12 and 24month.

#### 9.1.2 Freedom from TLR at 1, 12 and 24months

Freedom from TLR will be calculated using Kaplan-Meier analysis and will be estimated at 1, 12 and 24months.

### 9.2 Safety:

#### 9.2.1 Occurrence of device- or procedure-related serious adverse events and deficiencies

Among the valid subjects at procedure, 1, 12, 24, 36, 48 and 60months, the proportion of the subjects for whom the occurrence of serious adverse events were reported.

Serious Adverse events / SAE, regardless of their causal relationship with the device are the events fall under the below categories among the adverse events/ device deficiencies caused by the device. A SAE is classified by the physician who is responsible for the case.

- 1) Death
- 2) A case in which the event is suspected to cause a life-threatening condition.
- 3) A case that requires hospitalization in a hospital or a clinic or an extension of a hospital stay.
- 4) Disability
- 5) A case in which the event could have resulted in disability.
- 6) A case that is serious according to the cases in the above 1) to 5).
- 7) A congenital disease or abnormality from which a later generation of a patient will suffer.

Hospitalization without the onset of a new adverse event or aggravation of a pre-procedure complication, such as the reasons for hospitalization listed below, will not be handled as a serious adverse event.

- Hospitalization due to treatment that had previously been scheduled before the procedure by VIABAHN(hospitalization due to surgery for a pre-procedure complication that can be conducted after improvement of the target lesion)
- Administrative hospitalization (e.g. hospitalization for a regular medical checkup, examination, or training)
- Hospitalization at a rehabilitation facility

#### 9.2.2 Stent fracture

Stent fracture rate will be calculated using Kaplan-Meier analysis and will be estimated at 12, 24, 36, 48 and 60months. When an occurrence of fracture was suspected at sites, the image should be sent to Core lab for the assessment.

#### 9.3 Assessment period

Assessment windows are as below;

Table 2: Assessment period

Follow-up visit	Ideal allowance of follow-up window	Analysis window
Procedure	0	0
1 month	23~44	15~59
12 months	275~455	243~546
24 months	640~820	547~911
36 months	1005~1185	912~1275
48 months	1370~1550	1276~1640
60 months	1735~1855	1641~2006

#### 10. Organization for Operation of Post-Marketing Surveillance Study

The same as that written in Master Plan of Post-Marketing Surveillance Study

#### 12. Others

There is no other information to describe.

## 1.0 Introduction

This Statistical Analysis Plan (SAP) describes the statistical analyses planned to address the objectives of JPS 16-03. This SAP summarizes the analyses that will be performed to determine the safety and effectiveness of the GORE® VIABAHN® Endoprosthesis (VIABAHN®) when used for the treatment of patients with symptomatic peripheral arterial disease in superficial femoral arteries (SFA). This SAP outlines tables, figures, and listings that are included in reports for the JPS 16-03 Post-Marketing Surveillance.

## 2.0 Study Design Overview

### 2.1 Objectives

The objectives of JPS 16-03 is to document the efficacy and safety of the VIABAHN® for the treatment of patients with symptomatic peripheral arterial disease in the SFA.

### 2.2 Design Summary

This is a Japanese regulatory post-marketing surveillance to investigate the safety and effectiveness of VIABAHN®. The surveillance will continuously enroll all patients treated for symptomatic peripheral arterial disease with VIABAHN® at the participating institutions, until 250 patients with lesions longer than 15 cm have been enrolled. Patients who have the treatment of traumatic or iatrogenic vessel injury in thoracic abdominal, or pelvic arteries (except the aorta, coronary, brachiocephalic, aortic, vertebral and pulmonary arteries) with VIABAHN® will be excluded. Patients treated with VIABAHN® before conclusion of a contract will be enrolled in this surveillance retrospectively.

### 2.3 Data Analysis

#### *Efficacy*

**Primary assisted patency** at 12 and 24 months after implant will be estimated by Kaplan-Meier analysis.

**Freedom from Target Lesion Revascularization (TLR)** at 1, 12, and 24 months after implant will be estimated by Kaplan-Meier analysis.

#### *Safety*

**Occurrence of device or procedure related serious adverse events or deficiencies.** The number of events and subjects for which a reported serious adverse event occurred will be calculated at procedure and 1, 12, 24, 36, 48, and 60 months after implant.

**Stent fracture** rates will be estimated at 12, 24, 36, 48 and 60 months calculated using Kaplan-Meier analysis. When an occurrence of fracture is suspected at the site, the image will be sent to Core lab for assessment.

### 2.4 Statistical Hypotheses and Sample Size

CONFIDENTIAL INFORMATION

### 3.0 Study Data Collection

#### 3.1 Study Data Collection Intervals

Subjects will be asked to return for follow-up visits at 1, 12, 24, 36, 48, and 60 months. Evaluations and information to be collected at each visit is shown in Table 1.

Table 1: Examination schedule

Diagnostic Test	Procedure	1 Month	12 Months	24 Months	36 Months	48 Months	60 Months
Patient background and pre-operative patient information	X						
Date of discharge		X					
Device usage information	X						
Presence / absence of concurrent treatments and their detail if there was any	X						
Information on antiplatelet, anticoagulant drug administration	X	X	X	X			
Rutherford classification	X	X	X	X	X	X	X
ABI (or TBI)	X	X	X	X	X	X	X
CDUS			X	X	X	X	X
Plain X-ray			X	X	X	X	X
Adverse events and/or deficiencies and details	X	X	X	X	X	X	X

#### 3.2 Study Interval Windows

The visit windows and corresponding analysis windows are shown in Table 2.

Table 2: Assessment period

Follow-up visit	Visit Window (days)	Analysis Window (days)	Kaplan-Meier Window (days)
Procedure	0	0	0
1 month	23 - 44	1 - 37	1 - 30
12 months	275 - 455	38 - 395	31 - 365
24 months	640 - 820	396 - 760	366 - 730
36 months	1005 - 1185	761 - 1277	731 - 1095
48 months	1370 - 1550	1278 - 1642	1096 - 1460
60 months	1735 - 1855	1643 - 1855	1461 - 1825

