### 4.2 Timing of Analyses

Annual reports will be created on the anniversary of the approval date. A final analysis will be performed after all enrolled subjects complete the 60-month follow-up or have been withdrawn from the surveillance.

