## 6.0 Data Sets, Tables, Figures, and Listings

At a minimum, the follow set of Tables and Figures will be produced for the reports defined in section 4.2. Unless specified, the Tables and Figures will be analyzed using [REDACTED] All Subjects [REDACTED]

[REDACTED] Listings will be produced for the final report.

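### SAP Kaplan-Meier cut-offs fall inside the X-ray visit windows, so a stent fracture rate dated at the detecting image depends on visit timing and on a censoring rule that cannot be read

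*SAP*

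**What the plan says.** SAP section 3.2, Table 2, gives three windows per visit, in the order visit, analysis, Kaplan-Meier. The 12-month row reads "12 months 275 - 455 38 - 395 31 - 365", the 24-month row "24 months 640 - 820 396 - 760 366 - 730" and the 60-month row "60 months 1735 - 1855 1643 - 1855 1461 - 1825". The 36- and 48-month rows follow the 12-month pattern.

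Plain X-ray and CDUS are first scheduled at 12 months and then yearly (Protocol 8.1.3, 8.1.4 and Table 1). Stent fracture is the only focused survey item (Protocol 8.2). Its estimator is fixed in Protocol 9.2.2: "Stent fracture rate will be calculated using Kaplan-Meier analysis and will be estimated at 12, 24, 36, 48 and 60months". SAP 4.3 repeats this.

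The protocol's own table (9.3) has different analysis windows. Its 12-month row, visit window then analysis window, is "12 months 275~455 243~546".

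On reporting, SAP 4.2 says "Annual reports will be created on the anniversary of the approval date", and SAP 6.0 says "At a minimum, the follow set of Tables and Figures will be produced for the reports defined in section 4.2". The table list itself is redacted. Protocol 7 gives "Enrollment period: About five months".

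SAP 3.3 says which images go to the core lab, but not what date a fracture carries. No readable text gives an event-date or censoring rule for findings made on an image. Such a rule could sit in obscured text: the block under the TLR definition in SAP 4.3, or SAP 5.1 and 5.2.

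**The concern.** A fracture without symptoms is seen only when an X-ray is taken. A fully compliant 12-month X-ray on day 400 comes after the day-365 cut-off. If the fracture is dated at that image, it counts toward 24 months. Two sites with the same device and the same true fracture rate would then report different 12-month rates, because one sees patients a month early and the other a month late.

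Censoring can push the other way. If fracture-free subjects are censored at their last X-ray and that X-ray falls before the cut-off, they leave the risk set early. Fractures found in the remaining days are then divided by a shrinking denominator. This matters most for the newest visit in an annual report. With about five months of enrolment, most subjects share the same newest visit.

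At stake is the reported estimate for the focused survey item, in the annual reports as well as the final one.

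**Working it through.** The plan states no fracture rate, so there is no figure of its own to reproduce. Step 1 needs only the two window tables. The later steps rest on assumptions, stated where they enter.

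**1. Day counts (SAP Table 2).** Window length = end − start + 1. Days after the cut-off = visit-window end − Kaplan-Meier end.

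| Visit | Visit window | Length | KM end | Days after | Share |
|---|---|---|---|---|---|
| 12 m | 275–455 | 181 | 365 | 90 | 49.7% |
| 24 m | 640–820 | 181 | 730 | 90 | 49.7% |
| 36 m | 1005–1185 | 181 | 1095 | 90 | 49.7% |
| 48 m | 1370–1550 | 181 | 1460 | 90 | 49.7% |
| 60 m | 1735–1855 | 121 | 1825 | 30 | 24.8% |

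On-time images on days 1826–1855 belong to no Kaplan-Meier window. The SAP analysis windows also cut on-time visits: 455 − 395 = 60 days at 12 months and 820 − 760 = 60 days at 24 months pass to the next visit. The protocol's analysis windows (243–546, 547–911, 912–1275, 1276–1640, 1641–2006) hold every on-time visit.

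**2. The 12-month estimate by hand.** Assume 2% per year at constant hazard, F(d) = 1 − 0.98^(d/365), fractures dated at the detecting image, visits spread evenly over the window, and no dropout. In the final analysis nobody is censored before day 365, so the estimate is the share of visits on days 275–365 times F at their mean day, 320:

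(91/181) × (1 − 0.98^(320/365)) = 0.503 × 1.756% = 0.88%, against a true 2.00%.

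Simulation gives 0.9%. If every image were taken on day 365 the estimate would be right; if all were taken after it, the estimate would be 0.

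**3. Final analysis, other timings (simulation, censored at last image).**
- 12 months: 0.32% with visits centred 30 days late; about 1.5% with visits 30 days early; 1.80% with visits 45 days early (SD 20) and 10% dropout per visit.
- 24 to 60 months, even visits, no dropout: 2.88, 4.84, 6.72 and 10.04%, against 3.96, 5.88, 7.76 and 9.61%. The first three are low and the last is high.
- 20% dropout per visit, visits 30 days early: 6.0% at 36 months and 8.1% at 48 months, both too high.

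**4. Annual report with 12 months as the newest visit, visits 30 days early.** The estimate is 3.3% if subjects are censored at the last image, with only 13–17% still at risk at day 365. It is 1.5% if they are censored at the end of the visit window. The censoring rule alone reverses the direction.

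**5. Scale.** At 2% and n = 250 the expected count is 250 × 0.02 = 5 fractures. A range of 0.3% to 1.8% means a shift of 250 × 0.017 = 4.25 down to 250 × 0.002 = 0.5 fractures. The standard error is √(0.02 × 0.98/250) = 0.89 points, and the exact 95% interval for 5/250 is about 0.65% to 4.6%. The 250 counts subjects with long lesions; All Subjects may be more.

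**6. Indexing by scheduled visit.** With no dropout, the 12-month estimate is close to F at the mean visit day: F(335) = 1.84%, F(395) = 2.16%, F(320) = 1.76%. The errors are about 8%, 8% and 12% of 2.0%. Simulations with 0–30% dropout and visits up to 30 days early or late give 1.83–2.17% at 12 months and 9.4–9.7% at 60 months.

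**The case against.** **Redaction.** Everything beyond the day counts depends on dating and censoring rules that may be in obscured text. This stands. A reader might infer that the SAP has no such rule; the documents do not support that.

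**The cut-offs are the anniversaries.** Days 365, 730 and so on are what the protocol's 12- and 24-month estimates mean, and any visit window centred on an anniversary straddles it. That is true, and day-based Kaplan-Meier suits exactly dated events. It does not suit a finding made mainly at visits, about half of which may fall on either side of the cut-off.

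**Sampling error.** A shift of 1 to 4 fractures lies within the uncertainty of 250 subjects. This limits the practical weight. The shift is systematic, however, and would not show in the confidence interval.

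**Direction.** A reader might infer that the plan always understates fracture and so favours the device. It does not. Later and annual-report estimates can be too high, and even the final 12-month rate reached 2.03% in a stress run with 40% dropout, early visits and early onset.

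**The remedy is not uniformly better.** With visits 45 days early and 10% dropout, day-based estimates at 12 to 48 months are 1.80, 3.83, 5.87 and 7.85%, and visit-indexed ones 1.72, 3.66, 5.59 and 7.48%, against 2.00, 3.96, 5.88 and 7.76%. Day-based is slightly closer there, but far worse at 60 months (15.46% against 9.34%; true 9.61%). This stands as a limit on the benefit.

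**CDUS.** A reader might extend the same figures to patency. The documents do not allow it. TLR and symptomatic occlusions carry their own dates, and ABI or TBI also informs patency, so the size of any effect is unknown.

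**Conclusion.** The point holds in a conditional form. The day counts are certain: 90 of 181 on-time days at 12 to 48 months, and 30 of 121 at 60 months, come after the cut-off. If fractures are dated at the detecting image, the reported rates depend on visit timing and on the censoring rule as well as on the device.

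Under an assumed 2% per year, with censoring at the last image and the timings tried, the final 12-month estimate is about 0.3% to 1.8% against 2.0%. That is roughly 0 to 4 of 5 expected fractures in 250 subjects. No fixed direction can be claimed for later times or annual reports. No visible test or threshold depends on these rates, so the harm is to the reported estimates. It is worth fixing because the item is the surveillance's focus and the repair is cheap. Confidence is medium, because the true rate, the visit pattern and the redacted rules are unknown.

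**What to change.** - **Fracture on X-ray.** Assign each image to its scheduled visit with the protocol's contiguous analysis windows (243–546, 547–911, 912–1275, 1276–1640, 1641–2006). These also place images that miss the visit windows. Run Kaplan-Meier on scheduled visit, with fracture-free subjects censored at their last imaged visit. Days 60–242 lie in no protocol analysis window, so state a rule for an unscheduled X-ray there.
- **Sensitivity analysis.** Add an interval-censored (Turnbull) estimate from last negative to first positive image. This also handles a missed X-ray followed by a positive one.
- **TLR and patency.** Keep day-based Kaplan-Meier for TLR. For patency, keep exact dates for TLR and symptomatic occlusions, and treat loss seen only on CDUS as interval-censored in a sensitivity analysis.
- **Windows.** Reconcile the SAP analysis windows with the protocol's, and do not use the SAP's for the assignment while they move 60 of 181 on-time days at 12 and 24 months.
- **Redacted text.** If it already holds such a rule, refer to it from SAP Table 2.

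The cost is SAP wording and minor programming, with no new data and no departure from the protocol's Kaplan-Meier method. The 12-month fracture rate would probably become less favourable. A timing error of roughly 10% of that rate would remain. It is about 12% with visits 45 days early, and about 16% in a stress test with onset bunched in the first 200 days of each year.

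### Three SAP analysis windows (1, 12 and 24 months) close before their own visit windows and disagree with the protocol, so late but allowed visits count under the next visit

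*SAP*

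**What the plan says.** SAP section 3.2 introduces its table with "The visit windows and corresponding analysis windows are shown in Table 2". The columns are visit window, analysis window and Kaplan-Meier window, in days. Three of the rows are:

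- "12 months 275 - 455 38 - 395 31 - 365"
- "24 months 640 - 820 396 - 760 366 - 730"
- "36 months 1005 - 1185 761 - 1277 731 - 1095"

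The 1-month row has visit window 23-44 and analysis window 1-37. The last row is "60 months 1735 - 1855 1643 - 1855 1461 - 1825".

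Protocol section 9.3, Table 2 gives the same visit windows but other analysis windows, for example "12 months 275~455 243~546", "24 months 640~820 547~911" and "60 months 1735~1855 1641~2006". Its 1-month analysis window is 15-59.

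The SAP gives no visible reason for departing from the protocol. No visible text says which data the analysis-window column governs, or that visits are assigned by case report form rather than by day.

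**The concern.** An analysis window that corresponds to a visit should contain every day on which that visit is allowed. At 1, 12 and 24 months the SAP's does not, and the next window opens the day after it closes. A patient who attends late but within the rules is therefore counted at the following visit.

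What is exposed is any by-visit summary of the items in the examination schedule: ABI, Rutherford class, duplex ultrasound, plain X-ray and drug use. A patient seen on days 400 and 730, both allowed, would have no 12-month record and two 24-month records. The antiplatelet and anticoagulant item shows the mismatch most clearly. SAP Table 1 collects it at procedure, 1, 12 and 24 months only, yet a 24-month visit on days 761-820 is labelled 36 months, where neither that table nor protocol section 8.1.4 schedules it.

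The two documents also give different answers for the same visit date, in a surveillance that feeds annual reports and a final report.

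**Working it through.** **Inputs.** Visit windows are common to both documents. Analysis windows come from SAP Table 2 (section 3.2) and protocol Table 2 (section 9.3). Nominal days 30, 365, 730, 1095, 1460 and 1825 are the ends of the SAP's Kaplan-Meier windows.

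**Step 1: compare the two columns.**

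| Visit | Visit window | SAP analysis | Protocol analysis | SAP minus protocol (start, end) |
|---|---|---|---|---|
| 1 month | 23-44 | 1-37 | 15-59 | -14, -22 |
| 12 months | 275-455 | 38-395 | 243-546 | -205, -151 |
| 24 months | 640-820 | 396-760 | 547-911 | -151, -151 |
| 36 months | 1005-1185 | 761-1277 | 912-1275 | -151, +2 |
| 48 months | 1370-1550 | 1278-1642 | 1276-1640 | +2, +2 |
| 60 months | 1735-1855 | 1643-1855 | 1641-2006 | +2, -151 |

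All six rows differ. Four of the twelve bounds differ by only 2 days; the other eight differ by 14 to 205 days.

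**Step 2: count allowed days that fall outside their own analysis window.** Days allowed = visit end - visit start + 1. Days misplaced = visit end - SAP analysis end, where positive.

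- 1 month: allowed 44 - 23 + 1 = 22; misplaced 44 - 37 = 7 (days 38-44); 7/22 = 32%.
- 12 months: allowed 455 - 275 + 1 = 181; misplaced 455 - 395 = 60 (days 396-455); 60/181 = 33%.
- 24 months: allowed 820 - 640 + 1 = 181; misplaced 820 - 760 = 60 (days 761-820); 60/181 = 33%.
- 36, 48 and 60 months: 0.
- Protocol windows: 0 at all six visits.

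**Step 3: distance from the nominal days.** The misplaced 12-month days lie 396 - 365 = 31 to 455 - 365 = 90 days from their own nominal visit, and 730 - 455 = 275 to 730 - 396 = 334 days from the visit they are given to. The 24-month figures are the same. At 1 month they are 8-14 days against 321-327.

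**Step 4: two on-schedule visits in one window.** Pairs of allowed days for consecutive visits that share a SAP analysis window:

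- 1 and 12 months: 7 × 121 = 847 of 22 × 181 = 3982.
- 12 and 24 months: 60 × 121 = 7260 of 181 × 181 = 32761.
- 24 and 36 months: 60 × 181 = 10860 of 32761.
- Later pairs: 0. Under the protocol: 0 for all five pairs.

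**Step 5: where the SAP cuts fall.** Midpoints between nominal visits are (365 + 730)/2 = 547.5, then 912.5, 1277.5 and 1642.5. The SAP cuts lie at 395.5, 760.5, 1277.5 and 1642.5, so they are 152, 152, 0 and 0 days early. The window widths are 37, 358, 365, 517, 365 and 213 days. No rule requires midpoints, but the first two cuts do not follow the same rule as the last two.

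**Step 6: from days to visits (assumption).** The documents do not give the distribution of visit dates. Take visit timing as normal around the nominal day, conditional on being in the visit window, and rounded to whole days. The share of 12- or 24-month visits misplaced is then [Φ(90.5/SD) - Φ(30.5/SD)] / [Φ(90.5/SD) - Φ(-90.5/SD)]:

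| SD (days) | 15 | 20 | 30 | 45 |
|---|---|---|---|---|
| Share misplaced | 2.1% | 6.4% | 15.4% | 23.7% |

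**The case against.** The strongest reply is that no named endpoint is shown to be harmed. Patency, freedom from TLR and stent fracture are Kaplan-Meier estimates with their own column. The by-visit tables that could be affected are not visible, because the output specifications and table lists are redacted. If visits are keyed by case report form, the column does not touch them. This stands as a limit on the consequence, but it does not remove the conflict between two visible tables.

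A second reply is that the SAP column runs without a gap from day 1 to day 1855, which suits the placing of event onsets, so it need not contain the visit windows. That is possible, but the SAP does not say so, and it describes these windows as matching the visits. If that is their purpose, the SAP must state it and must still say what places visit data.

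A third is that the protocol's windows are not a clean replacement: days 1-14 and 60-242 fall in none of them. This is right, and it is why they should be used for visit-based data only, not for event dates.

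Finally, the 2% to 24% range rests on assumed timing and gives only a rough idea of size. The 2-day differences are trivial, and the missing SAP window for days 1856-2006 matters only for visits after the 60-month visit window closes.

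**Conclusion.** The concern holds and should be fixed. As written, three SAP analysis windows exclude about a third of the days on which their own visits are allowed and pass those visits to the next time point, and the whole column differs from the protocol's. The table mismatch is certain.

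The practical effect is conditional on by-visit summaries being assigned by this column, and its size depends on visit timing that the documents do not give. No bias in the Kaplan-Meier endpoints is claimed, and any effect on serious adverse event counts cannot be determined from the visible text.

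**What to change.** For visit-based data, replace the SAP analysis-window column with the protocol's: 15-59, 243-546, 547-911, 912-1275, 1276-1640 and 1641-2006. Both documents then carry the same table, and every visit window lies inside its analysis window.

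Add two statements to the SAP:

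- Which record is used when two visits fall in one window. This can still happen when a visit is off schedule, for example days 560 and 730.
- Which contiguous intervals place serious adverse events by onset date. The choice is the sponsor's; the protocol's windows do not suit it because of their gaps.

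The cost is one table column and two sentences, with no new data and no burden on patients. The small downside is that visits on days 1-14 or 60-242 would be listed as unscheduled.
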